	
 4. Presence of preexisting advanced chronic renal failure (i.e., ESRD) requiring chronic renal replacement therapy prior to this episode of acute kidney injury or with pre-existing chronic kidney disease (CKD) defined as an eGFR<30 ml/min/1.73m². Patients who have never seen a pediatric nephrologist will be assumed not to have pre-existing CKD. 5. AKI occurring in the setting of burns, obstructive uropathy, scleroderma renal crisis, atheroembolism, functional or surgical nephrectomy, cyclosporine, or tacrolimus nephrotoxicity. 6. Metastatic malignancy which is actively being treated or may be treated by chemotherapy or radiation during the subsequent three month period after study therapy. 7. Chronic immunosuppression with the exception of corticosteroids up to a dose of 10 mg per day. 8. Known positive HIV or AIDS or COVID-19 9. Current Do Not Attempt Resuscitation (DNAR), Allow Natural Death (AND), or withdrawal of care status, or anticipated change in status within the next 7 days. 10. Patient not expected to survive 28 days because of an irreversible medical condition. (This is not restrictive to AKI, and may include situations such as the presence of irreversible brain damage, untreatable malignancy, inoperable life threatening condition, or any condition to which therapy is regarded as futile by the PI.) 11. Any medical condition that the Investigator thinks may interfere with the study objectives. 12. Treating clinician does not feel it is in the best interest of the patient 13. Platelet count <15,000/mm³ at time of screening. 14. Concurrent enrollment in another interventional clinical trial. Patients enrolled in clinical trials where only measurements and/or samples are taken (NO TEST DEVICE OR TEST DRUG USED) are allowed to participate. 15. Use of any other investigational drug or device within the previous 30 days. 16. Use of an AN-69 hemofilter membranes
Evaluation Plan	The primary evaluation of this study will be safety and all-cause mortality or dialysis dependency through 60 days post-enrollment. Additional endpoints will be time on CRRT, total ICU and hospital days. Mortality and dialysis dependency rates will be compared to historical controls.

LIST OF ABBREVIATIONS

ACD-A	Anticoagulant Citrate Dextrose- Formula A
AE	Adverse Event
AKI	Acute Kidney Injury
AIDS	Acquired Immunodeficiency Syndrome
AND	Allow Natural Death
ARDS	Acute Respiratory Distress Syndrome
ARF	Acute Renal Failure

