- Evidence of leakage (i.e., cracking/breakage of a port, connector, hemofilter cartridge or tubing).
- Any unforeseen malfunction that results in the need for discontinuation.

This trial is an early safety efficacy study but is not powered for statistical significance. Insights into a comparison of historical controls matched to SCD treated subjects will utilize the ppCRRT Registry to match for: etiology of AKI, co-morbidities, CRRT modality, dose and form of anticoagulant, adverse events. [10]

The ppCRRT Registry has data fields for the primary reason for CRRT, including AKI and its cause, as well as co-morbidities which will be matched for primary organ system involvement. The CRRT modality was evenly distributed between convective and diffusive modality, with 60% of the convective modalities provided as CVVH and 40% as CVVHDF. The anticoagulant protocol will be standardized with ACD-A/CaCl₂ and all centers

used the same protocol in ppCRRT Registry as outlined in this study protocol. Thus, the ppCRRT Registry dataset will be able to be matched to our study subject cohort. Also as noted above, subjects will be matched for age, size and PRISM II score.

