5.2 INCLUSION CRITERIA

1. The patient's parent or legal representative has provided informed consent.
2. Must be receiving medical care in an intensive care unit (e.g., PICU, CICU).
3. Age less than 18 years.
4. Body weight between ≥ 10 and ≤ 20 kg
5. Intent to receive full supportive care through aggressive management utilizing all available therapies for a minimum of 96 hours.
6. Clinical diagnosis of AKI requiring CRRT. AKI is defined as acute kidney injury with any one of the following:
 - Increase in SCr by ≥ 0.3 mg/dL (≥ 26.5 μ mol/L) within 48 hours or;
 - Increase in SCr to ≥ 1.5 times baseline, which is known or presumed to have occurred within the prior 7 days or;
 - Urine volume <0.5 ml/kg/h for 6 hours
7. At least one non-renal organ failure (defined as receiving mechanical ventilation or at least one vasoactive medication to treat hypotension) OR presence (proven or suspected) of sepsis. Sepsis is defined as at least two of the following criteria in the setting of a probable or documented infection^[29]:

Age	1mo-1yr	2-5 yr	6-12 yr	13-17 yr
Tachypnea (breaths/min) or mechanical ventilation not related to underlying neuromuscular disease of the receipt of general anesthesia	> 49	> 22	> 18	> 14
Tachycardia (beats/min)	> 150	> 140	> 130	> 110
Bradycardia if <1 yr (beats/min)	< 109			
Hyper or Hypothermia			> 38.5°C or < 36°C	
WBC ($\times 10^3/\text{mm}^3$)	> 17.5 or < 5	> 15.5 or < 6	> 13.5 or < 4.5	> 11 or < 4.5

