5.3 EXCLUSION CRITERIA

1. Threshold blood pressure of 80/40 mmHg-- patients with both a systolic blood pressure of less than 80 mmHg and a diastolic blood pressure of less than 40 mmHg.
2. Patients with a solid organ transplant or those with a bone marrow or stem cell transplant in the previous 100 days or who have not engrafted.
3. Acute or chronic use of circulatory support device, other than ECMO, such as LVADs, RVADs, BIVADs.
4. Presence of preexisting advanced chronic renal failure (i.e., ESRD) requiring chronic renal replacement therapy prior to this episode of acute kidney injury or with pre-existing chronic kidney disease (CKD) defined as a eGFR<30 ml/min/1.73m². Patients who have never seen a pediatric nephrologist will be assumed not to have pre-existing CKD.
5. AKI occurring in the setting of burns, obstructive uropathy, scleroderma renal crisis, atheroembolism, functional or surgical nephrectomy, cyclosporine or tacrolimus nephrotoxicity.
6. Metastatic malignancy which is actively being treated or may be treated by chemotherapy or radiation during the subsequent three month period after study therapy.
7. Chronic immunosuppression with the exception of corticosteroids up to a dose of 10 mg per day.
8. Known positive HIV or AIDS or COVID-19
9. Current Do not Attempt Resuscitation (DNAR), Allow Natural Death (AND), or withdrawal of care status, or anticipated change in status within the next 7 days.
10. Patient not expected to survive 28 days because of an irreversible medical condition. (This is not restrictive to AKI, and may include situations such as the presence of irreversible brain damage, untreatable malignancy, inoperable life threatening condition, or any condition to which therapy is regarded as futile by the PI.)

11. Any medical condition that the Investigator thinks may interfere with the study objectives.
12. Treating clinician does not feel it is in the best interest of the patient.
13. Platelet count <15,000/mm³.
14. Concurrent enrollment in another interventional clinical trial.
Patients enrolled in clinical trials where only measurements and or samples are taken (NO TEST DEVICE OR TEST DRUG USED) are allowed to participate.
15. Use of any other investigational drug or device within the previous 30 days.
16. Use of AN-69 hemofilter membranes

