Besides the test of the hypothesis the study is focused on observable, empirical and laboratory determinations of subject safety while on the SCD. Previous human trials have been conducted on the SCD device and the protocol contains a review of AE and SAE data from all SCD human studies and findings from those studies contributed to constructing the investigative safety profile. Safety endpoint measures specified in the protocol include adverse events, laboratory safety parameters, vital signs, ventilation status and hemodynamic variables. Device integrity and performance measurements are also defined as are circumstances which demand premature termination of SCD treatment.

Prolonged exposure to the SCD is anticipated to result in superior outcomes, although as noted above, this pilot study is not designed to assess for efficacy. However, we understand that a minimum amount of exposure to the SCD will be required for an appropriate safety analysis and for making any inference regarding efficacy. The ppCRRT experience demonstrated that the majority of patients (201/370) received CRRT for 1 to 7 days and exhibited 65% survival (Symons et al CJASN 2007 Table7).

This trial is an early safety efficacy study but is not powered for statistical significance. Insights into a comparison of historical controls matched to SCD treated subjects will utilize the ppCRRT Registry to match for: etiology of AKI, co-morbidities, CRRT modality, dose and form of anticoagulant, adverse events. [10]

The ppCRRT Registry has data fields for the primary reason for CRRT, including AKI and its cause, as well as co-morbidities which will be matched for primary organ system involvement. The CRRT modality was evenly distributed between convective and diffusive modality, with 60% of the convective modalities provided as CVVH and 40% as CVVHDF. The anticoagulant protocol will be standardized with ACD-A/CaCl₂ and all centers used the same protocol in ppCRRT Registry as outlined in this study protocol. Thus, the ppCRRT Registry dataset will be able to be matched to our study subject cohort. Also as noted above, subjects will be matched for age, size and PRISM II score.

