The Prospective Pediatric CRRT (ppCRRT) database will be used as a control for the CRRT treatment related factors including: patient age, gender, primary cause of AKI, total treatment duration, CRRT modality (CVVH, CVVHD, CVVHDF), CRRT small solute clearance (ml/1.73m²/hour), baseline estimated GFR (using the original Schwartz formula, which was used in the ppCRRT), urine output in the 24 hours prior to CRRT initiation (ml/kg/hour), percent fluid overload at CRRT initiation based on admission ICU weight, vasoactive medication number at time of CRRT initiation and mean airway pressure at CRRT initiation.

An additional analysis will also evaluate patients who have achieved targeted iCa levels during 90% of treatment time and those who do not.

In summary this protocol meets all criteria necessary for clinical scientific inquiry related to a test of hypothesis in a well monitored environment focused on subject safety during the conduct of the study. Basic statistics will be performed on the data sets along with historical data comparisons and subjected to subset analysis where appropriate. The results will help to guide the design of a future pivotal study of this device.

The rational for therapy, study objectives and endpoints, design, inclusion and exclusion criteria are explicitly defined. Subject safety parameters are well documented including safety reporting, safety observations and assays, procedures for subject withdrawal and study discontinuation criteria along with monitoring device integrity and performance. Lastly, a review of all prior SCD human study safety data is included in the protocol for full disclosure to study investigators and the informed consent document includes a full description of all known and potential risks of the device treatment.

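### Registry controls are matched on characteristics but not restricted to children who meet the trial's entry criteria, so they may include children the trial would have refused

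*Combined protocol and SAP*

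**What the plan says.** The synopsis (Evaluation Plan) states: "Mortality and dialysis dependency rates will be compared to historical controls". Section 3.1 puts a comparison with historic data into the primary objective, covering in-hospital mortality and mortality and dialysis dependency at days 28 and 60. Section 3.2 names all-cause mortality as the primary efficacy measure.

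The control group is described only through lists of variables:

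- Section 3.2 uses the registry to "match for: etiology of AKI, co-morbidities, CRRT modality, dose and form of anticoagulant, adverse events". Co-morbidities are matched at the level of the main organ system involved. It adds that "subjects will be matched for age, size and PRISM II score".
- Section 12 repeats this: "Insights into a comparison of historical controls matched to SCD treated subjects will utilize the ppCRRT Registry".
- Section 12 then says the registry "database will be used as a control for the CRRT treatment related factors including: patient age, gender, primary cause of AKI, total treatment duration". That list continues with CRRT modality and clearance, baseline eGFR, urine output, fluid overload, number of vasoactive drugs and mean airway pressure.

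The treated children, by contrast, pass through the entry criteria of sections 5.2 and 5.3. Inclusion 5 requires "Intent to receive full supportive care through aggressive management utilizing all available therapies for a minimum of 96 hours". Exclusion 9 removes children with a DNAR or AND order or "withdrawal of care status, or anticipated change in status within the next 7 days". Exclusion 10 removes any "Patient not expected to survive 28 days because of an irreversible medical condition". Exclusion 12 gives the treating clinician a veto. Exclusions 2, 5 and 6 remove certain transplant recipients, certain causes of AKI, and metastatic malignancy that is being or may soon be treated. Inclusion 7 requires ventilation, a vasoactive drug, or sepsis.

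**The concern.** Matching makes two groups alike on the variables named. It does not remove from the control side the children who would have failed the trial's entry rules on other grounds. Several of those rules select on expected outcome: limits on care, expected death within 28 days, a clinician's judgement. None of these is a matching variable. PRISM II as set out in Appendix A scores acute physiology. It has no item for limits of care or for malignancy, although its coma score and pupil items may partly reflect brain injury.

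If such children are removed from the treated group only, control mortality is raised by deaths that could not have occurred in the trial. A device with no effect could then appear to lower mortality, and death or dialysis with it. Section 12 says the results will help to design a future pivotal study, so the error could carry into that study's assumptions.

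**Working it through.** The plan gives no power, alpha or effect-size figure for the registry comparison, so there is no stated result to reproduce. The check has two parts.

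**1. Entry criteria set against the matching lists**

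| Entry criterion | Covered by matching or control variables? | Likely direction if not applied to controls |
|---|---|---|
| Full support intended for 96 hours (incl. 5) | No | Favours SCD |
| DNAR, AND or withdrawal of care (excl. 9) | No | Favours SCD |
| Not expected to survive 28 days (excl. 10) | Not directly; PRISM II in part | Favours SCD |
| Clinician veto (excl. 12) | No | Favours SCD |
| Transplant; treated metastatic malignancy (excl. 2, 6) | Partly, by co-morbidity; organ-system matching need not remove them | Favours SCD |
| Excluded AKI causes (excl. 5) | Largely, by cause of AKI | Unknown; no mortality figure given |
| Weight and age (incl. 3, 4) | Largely, by size and age | Not established |
| Organ failure or sepsis (incl. 7) | Partly, by vasoactive number and mean airway pressure | Probably against SCD |

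**2. Illustrative size**

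Let M be mortality in unscreened controls, p the share of them the trial would have refused, and q the mortality of that share.

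- Mortality in eligible controls: E = (M − pq) / (1 − p)
- Artefact: M − E = p(q − M) / (1 − p)

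The sign depends only on whether q exceeds M. Refused children who die more often than average produce a false benefit. Children without organ failure or sepsis who die less often produce the opposite.

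Inputs:

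- M = 35%. This is the complement of the 65% survival that section 12 quotes for registry children on CRRT for 1 to 7 days (201 of 370, or 54.3%). That group is a subset, so using 35% for the controls is an assumption.
- p = 5% to 20% and q = 70% to 90%. Both are assumptions; the documents give neither.

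Results:

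- p = 5%, q = 70%: (0.35 − 0.035) / 0.95 = 33.2%; artefact 1.8 points
- p = 5%, q = 90%: (0.35 − 0.045) / 0.95 = 32.1%; artefact 2.9 points
- p = 20%, q = 70%: (0.35 − 0.14) / 0.80 = 26.25%; artefact 8.75 points
- p = 20%, q = 90%: (0.35 − 0.18) / 0.80 = 21.25%; artefact 13.75 points

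With M = 50%, the approximate ICU mortality given in the synopsis, the ends of the range are (0.50 − 0.035) / 0.95 = 48.9% (1.1 points) and (0.50 − 0.18) / 0.80 = 40.0% (10.0 points).

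For scale, 3 deaths in 10 children has an exact 95% interval of 6.7% to 65.2%.

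**The case against.** Three stronger readings are tempting, and the documents support none of them.

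- *That the controls do include children the trial would have refused.* The registry's entry rules and its data on care limitation are not described. Section 3.2 also refers back to matching already noted, with no antecedent in the available text, and some pages are not available. The most that can be said is that controls may include such children.
- *That every mismatch favours SCD.* Inclusion 7 makes the trial population sicker. Leaving it unapplied would admit controls who are probably at lower risk. The direction for excluded AKI causes is unknown. The net sign over all criteria is not shown.
- *That the bias is 2 to 14 points.* Those figures depend on assumed inputs and treat the controls as an unselected pool. Matched controls may contain a smaller refused share than the whole registry.

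It is also fair to say that the matching already does much of the work for AKI cause, age and size, and some of it for organ failure. The criteria with the clearest direction are the hardest to apply retrospectively, so a filter will not remove all of the bias. Finally, the plan describes an unpowered pilot of at most 10 children, and the random error is far larger than the illustrated bias.

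These arguments limit the claim but do not remove it. Organ-system matching does not specifically exclude transplant or treated-malignancy controls, care limitation is not addressed at all, and a systematic error does not become harmless because the sample is small.

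**Conclusion.** The concern holds in a limited form. Followed as written, the control plan can admit registry children whom the trial would have refused. For the prognosis and care-limitation criteria, including transplant and treated metastatic malignancy, the likely bias favours SCD on mortality and on death or dialysis. That direction rests on refused children dying more often than eligible ones. For the organ-failure-or-sepsis requirement the bias probably runs the other way. Matching may reduce both.

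The size cannot be estimated from the documents. The range of about 2 to 14 points shows what the assumed inputs would imply and should not be cited as an estimate. The point does not invalidate the study, but it should be settled before the historical comparison is run and used to plan a pivotal trial.

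**What to change.** Add to the analysis plan, before the matching step, a restriction of the registry to children who meet every inclusion and exclusion criterion its fields support. Candidates are weight, age, ventilation or vasoactive drug or sepsis, transplant, malignancy, excluded causes of AKI, and care limitation if recorded. Section 3.2 says the registry holds the cause of AKI and co-morbidities; the availability of the other fields needs checking.

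Then list the criteria that cannot be applied, probably intent of care, expected 28-day survival and the clinician's veto. State that the remaining bias from these prognosis-based criteria favours SCD. If limitation or withdrawal of care is recorded, add a sensitivity analysis that excludes controls with it. Report how many registry children each criterion removes.

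The cost is some plan wording, a data filter, a smaller control pool and a little more analysis. No treatment or visit changes.

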4. STUDY DESIGN

This is an open-label, multi-center Pilot Study.

5. SELECTION OF PATIENT POPULATION

5.1 STUDY POPULATION

Up to 10 pediatric patients with a clinical diagnosis of AKI requiring CRRT will be enrolled in this study, in up to 7 Clinical Centers in the United States.

Pediatric patients with a body weight (BW) between ≥ 10 and ≤ 20 kg receiving care in the Intensive Care Units of each participating hospital will be screened daily and identified for participation in the trial.

5.2 INCLUSION CRITERIA

1. The patient's parent or legal representative has provided informed consent.
2. Must be receiving medical care in an intensive care unit (e.g., PICU, CICU).
3. Age less than 18 years.
4. Body weight between ≥ 10 and ≤ 20 kg
5. Intent to receive full supportive care through aggressive management utilizing all available therapies for a minimum of 96 hours.
6. Clinical diagnosis of AKI requiring CRRT. AKI is defined as acute kidney injury with any one of the following:
 - Increase in SCr by ≥ 0.3 mg/dL (≥ 26.5 μ mol/L) within 48 hours or;
 - Increase in SCr to ≥ 1.5 times baseline, which is known or presumed to have occurred within the prior 7 days or;
 - Urine volume <0.5 ml/kg/h for 6 hours
7. At least one non-renal organ failure (defined as receiving mechanical ventilation or at least one vasoactive medication to treat hypotension) OR presence (proven or suspected) of sepsis. Sepsis is defined as at least two of the following criteria in the setting of a probable or documented infection^[29]:

Age	1mo-1yr	2-5 yr	6-12 yr	13-17 yr
Tachypnea (breaths/min) or mechanical ventilation not related to underlying neuromuscular disease of the receipt of general anesthesia	> 49	> 22	> 18	> 14
Tachycardia (beats/min)	> 150	> 140	> 130	> 110
Bradycardia if <1 yr (beats/min)	< 109			
Hyper or Hypothermia			> 38.5°C or < 36°C	
WBC ($\times 10^3/\text{mm}^3$)	> 17.5 or < 5	> 15.5 or < 6	> 13.5 or < 4.5	> 11 or < 4.5

5.3 EXCLUSION CRITERIA

1. Threshold blood pressure of 80/40 mmHg-- patients with both a systolic blood pressure of less than 80 mmHg and a diastolic blood pressure of less than 40 mmHg.
2. Patients with a solid organ transplant or those with a bone marrow or stem cell transplant in the previous 100 days or who have not engrafted.
3. Acute or chronic use of circulatory support device, other than ECMO, such as LVADs, RVADs, BIVADs.
4. Presence of preexisting advanced chronic renal failure (i.e., ESRD) requiring chronic renal replacement therapy prior to this episode of acute kidney injury or with pre-existing chronic kidney disease (CKD) defined as a eGFR<30 ml/min/1.73m². Patients who have never seen a pediatric nephrologist will be assumed not to have pre-existing CKD.
5. AKI occurring in the setting of burns, obstructive uropathy, scleroderma renal crisis, atheroembolism, functional or surgical nephrectomy, cyclosporine or tacrolimus nephrotoxicity.
6. Metastatic malignancy which is actively being treated or may be treated by chemotherapy or radiation during the subsequent three month period after study therapy.
7. Chronic immunosuppression with the exception of corticosteroids up to a dose of 10 mg per day.
8. Known positive HIV or AIDS or COVID-19
9. Current Do not Attempt Resuscitation (DNAR), Allow Natural Death (AND), or withdrawal of care status, or anticipated change in status within the next 7 days.
10. Patient not expected to survive 28 days because of an irreversible medical condition. (This is not restrictive to AKI, and may include situations such as the presence of irreversible brain damage, untreatable malignancy, inoperable life threatening condition, or any condition to which therapy is regarded as futile by the PI.)

11. Any medical condition that the Investigator thinks may interfere with the study objectives.
12. Treating clinician does not feel it is in the best interest of the patient.
13. Platelet count <15,000/mm³.
14. Concurrent enrollment in another interventional clinical trial.
Patients enrolled in clinical trials where only measurements and or samples are taken (NO TEST DEVICE OR TEST DRUG USED) are allowed to participate.
15. Use of any other investigational drug or device within the previous 30 days.
16. Use of AN-69 hemofilter membranes

